Once the patient is consented for the study, randomization will then be performed using stratified (based on location of the tumor – head/neck vs. body/tail) block randomization. The patients will undergo Linear EUS, as previously described by Devila Fejardo et al. and have fiducial marker placement via a traditional 22G back-loaded needle (Visicoil) [22] or the new 22G preloaded needle (PreLoad4). Multiple endpoints will be recorded, including total length of procedure, how many markers are successfully deployed, and technical success (Ease of passage of delivery system, ease of deployment of fiducials, EUS visualization of delivery system needle, EUS visual appearance of fiducials, and time for fiducial placement defined as starting time of removing the needle from its packaging and ending time as removal of needle after final marker deployment). Procedure time will be recorded by a research assistant at each site. Fiducial marker location will be confirmed via fluoroscopy at time of placement and on 4D treatment planning CT ordered by the radiation oncologist for simulation.

Patients will be discharged home after post procedure recovery. Patients will be contacted at home by a research coordinator or endoscopy staff 24-48 hours and 7-10 days after the procedure to document any

immediate and delayed complications. Patients will return for their IGRT visit, and any evidence of fiducial marker migration will be recorded by the radiation oncologist.

For patients who have preceding diagnostic FNA, this will be recorded, with number of passes/aspiration attempts recorded as well.

Endpoints

Primary endpoints utilized in this study will be:

• To compare procedure time of 22G needle placement of three Visicoil fiducial markers and 22G needle preloaded fiducial markers.

Secondary endpoints will include:

- Technical success of fiducial marker placement in 22G back-loaded needles and 22G preloaded needles defined by proper placement of three fiducial markers in a pancreatic neoplasm.
- Rate of fiducial migration
- Ease of passage of delivery system
- Ease of fiducial deployment
- EUS visual appearance of fiducials
- Visualization as assessed by radiation oncology
- Inadvertent deployment of fiducials
- Adverse event rates recorded throughout the study period
- Descriptive comparison of outcomes across sites

Figure 1- Proposed Study Methods

C. Description, Risks, and Justification of Procedures and Data Collection Tools.

Recording of Complications

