Complications will be defined as any deviation from the clinical course after the procedure. All adverse event data will be collected during the study period and graded as:

Minor: nausea, vomiting, abdominal pain

Major: perforation, pancreatitis, major bleeding, infection, transfusion secondary to major bleeding, aspiration, arrhythmia, hypotension, death

The investigator at each site will assess each adverse event with respect to severity and relationship to the study interventions. Patients will be contacted at 24-48 hours post-procedure by an experienced GI nurse to assess for complications post procedure (See Appendix AP5/6). All adverse events (whether or not considered device-related) must be reported immediately (within 48 hours) to the study coordinator, confirmed in writing by the Investigator and recorded in the Adverse Events section of the case report form (CRF). Those adverse events that meet the criteria for a Serious Adverse Event will be reported additionally on a Serious Adverse Event CRF. The investigator at each site will make the determination regarding reportability of any AE or SAE to their respective IRB. The University of Colorado will be the central site for all SAE reporting at any site within 24 hours of the occurrence. They will also control randomization, and receive/manage AE/SAE reporting and DSMC. A group of PIs at the cancer center DSMC will review all reports every 6 months. SAE reporting will be reviewed within 24 hours, and all sites and IRBs (per IRB policy) will be informed within a 12-24 hour period of the event and review regarding whether the SAE was thought to be potentially related to the study/new device.

Monitoring and Oversight

The sponsor investigator will be responsible for monitoring the trial per the trial monitoring plan, in addition to overseeing the safety and efficacy of the trial including any specimens collected, executing the data and safety monitoring (DSM) plan, and complying with all reporting requirements to local and federal authorities. This oversight will be accomplished through additional oversight from the Data and Safety Monitoring Committee (DSMC) at the University of Colorado Cancer Center (CU Cancer Center). The DSMC is responsible for ensuring data quality and study participant safety for all clinical studies at the CU Cancer Center, which is the coordinating institution of this trial. A summary of the DSMC's activities is as follows:

- Conduct of internal audits

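### Adverse event calls may be made by endoscopy staff who may know which needle was used, and no masking of patient, caller or assessor is stated, so minor symptom rates are open to unequal probing; a cheap change would reduce this.

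*Protocol*

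**What the plan says.** The protocol describes post-discharge follow-up in two places, and they name different callers.

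- Section 2.B, procedure description: "Patients will be contacted at home by a research coordinator or endoscopy staff", once at 24-48 hours and again at 7-10 days.
- Section 2.C, Recording of Complications: "Patients will be contacted at 24-48 hours post-procedure by an experienced GI nurse to assess for complications post procedure". This section names no caller for the 7-10 day contact.

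Section 2.C defines what is collected and who judges it.

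- Definition: "Complications will be defined as any deviation from the clinical course after the procedure".
- Minor grade: "nausea, vomiting, abdominal pain".
- Major grade: "perforation, pancreatitis, major bleeding, infection, transfusion secondary to major bleeding, aspiration, arrhythmia, hypotension, death".
- Assessor: "The investigator at each site will assess each adverse event with respect to severity and relationship to the study interventions".

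Adverse event rates are part of hypothesis 2 and are the whole of the second secondary aim (section 1.2). The Data Analysis Plan (section 2.E) compares them between arms with Fisher's exact test; the SAP allows chi-square or Fisher. The opaque sealed envelopes under Randomization conceal the assignment before it is made. They do not bear on who knows the arm afterwards.

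**The concern.** The endoscopist cannot be masked to the needle, but the patient and the person who telephones the patient can be. The plan does not use that opportunity. It allows the calls to be made by endoscopy staff, a group that may include people who were present at the procedure, and nothing says that the arm is kept from the caller or the patient.

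Every minor event is a symptom. Once the patient has gone home, whether it is counted depends largely on how the question is asked and how far it is pursued. The definition of a complication is open-ended, which leaves further room for judgement. One arm uses a new device, so closer questioning in that arm, or less of it, is plausible.

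The trial hopes to show that adverse event rates are comparable, and no margin for comparability is given. Fuller capture in one arm could create an apparent difference. Poorer capture in the arm with more events could hide a real one and make the arms look alike.

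**Working it through.** **1. Who may know the arm**

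| Role | What the protocol says | Masking stated? |
|---|---|---|
| Patient | Consented, randomized, telephoned twice | No |
| Caller, 24-48 hours | Coordinator or endoscopy staff (2.B); GI nurse (2.C) | No |
| Caller, 7-10 days | Coordinator or endoscopy staff (2.B); not named in 2.C | No |
| Assessor of severity and relationship | Site investigator (2.C) | No |

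Knowledge of the arm is permitted at every step. It is not asserted at any.

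**2. Which events depend on the calls**

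Section 2.C lists 3 minor terms and 9 major terms, 12 in all. The 3 minor terms are symptoms. The 9 major terms are mostly clinical diagnoses or documented events. The concern therefore bears on the minor category. No expected frequencies are given.

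**3. Size of one event**

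Input: 20 patients per arm (Sample Size in section 2.E; SAP). One event is 1/20 = 5 percentage points; two are 2/20 = 10 points. The event rates below are assumptions, because the documents give none.

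| True counts, equal in both arms | Observed after one-sided loss | Difference | Fisher p, two-sided |
|---|---|---|---|
| 4/20 (20%) | 4/20 vs 3/20 (15%) | 5 points | 1.00 |
| 4/20 (20%) | 4/20 vs 2/20 (10%) | 10 points | 0.66 |
| 2/20 (10%) | 2/20 vs 1/20 (5%) | 5 points | 1.00 |

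At a true rate of 10%, one missed event halves the observed rate. In none of these cases does the test result change. Even 4/20 vs 0/20 gives p = 0.11. A single event crosses 0.05 only from an already lopsided table; for example, 5/20 vs 0/20 gives p = 0.047.

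**4. Would the planned test reveal unequal capture?**

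Assume equal true rates, with a proportion c1 of events captured in one arm and c2 in the other. The apparent difference is true rate × (c1 − c2). The rejection probability is exact for Fisher's test at 20 per arm and 0.05 two-sided.

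| True rate | 90% vs 70% capture: difference; rejection | 90% vs 50% capture: difference; rejection |
|---|---|---|
| 10% | 2 points; 0.9% | 4 points; 1.1% |
| 20% | 4 points; 2.8% | 8 points; 5.2% |
| 30% | 6 points; 3.7% | 12 points; 8.7% |
| 40% | 8 points; 4.7% | 16 points; 12.8% |

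For comparison, the 95% half-width of a difference is 1.96 × √(2p(1−p)/20): 18.6 points at p = 10% and 28.4 points at p = 30%. Most of the distortions above lie well inside the sampling error. They would rarely produce a significant result, and for the same reason they would rarely be noticed.

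**The case against.** The strongest reply is that the effect is small. The outcome is secondary, the distortion is smaller than the sampling error in all the cases shown, and one or two events would hardly ever change the test. That stands. A reader might infer that a symptom or two would settle the comparison; the Fisher results show otherwise. What remains is a possible shift in the reported rates, and in a trial this small those rates will carry much of the interpretation.

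Three other strong readings also fail on the text.

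- A reader might infer that adverse events here are largely patient-reported. Only 3 of the 12 listed terms are symptoms of that kind, and no frequencies are given.
- A reader might infer that callers know the arm. The protocol does not say so: a coordinator may call, and nothing places the nurse in the procedure room.
- A reader might infer that masking would be free. It needs a caller from outside the room at each site.

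Some protection already exists. Minor and major are set by named terms, so the grade of nausea does not depend on who assigns it. Events are reported whether or not they are thought device-related, so a biased attribution does not remove them from the count. Section 2.C provides for checking case report forms against source documents. Appendices AP5/6 are listed for adverse event collection; if they are a structured form used alike in both arms, they already limit unequal probing. The appendices and consent text are not in the supplied documents, so this cannot be checked, and the point rests on the main text. None of these protections governs how far a caller pursues a symptom that the patient has not volunteered.

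**Conclusion.** The point holds as a modest design improvement. The plan permits adverse event calls by staff who may know the arm, names different callers for the same contact, and states no masking of patient, caller or assessor. Unequal probing could move observed minor-event rates by 5 points per event at 20 per arm. Under the assumed true rates of 10% to 40%, capture of 90% against 70% gives an apparent difference of 2 to 8 points, and 90% against 50% gives 4 to 16 points. Both the event rates and the capture proportions are assumptions; the documents supply neither.

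The bias could act in either direction on the comparison behind hypothesis 2 and the second secondary aim. It would rarely change the Fisher test, and it does not touch the primary endpoint. The documents do not show that such bias occurred, only that the plan leaves room for it.

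**What to change.** Reconcile sections 2.B and 2.C so that they name the same caller for each contact, and specify the following.

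- Both calls are made by a research coordinator or a nurse who was not in the procedure room and is not told the arm.
- The same AP5/6 collection form is used in both arms, and the arm does not appear on it.
- The patient is not told which needle was used until the 7-10 day call is complete.
- The treating team and those handling serious adverse event reports have full access to the arm at any time.
- Minor event rates are compared as recorded on the masked call form.

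Masked grading should not be claimed where the site investigator was the operator, since that person already knows the arm. The report should acknowledge that severity and relationship judgements may be unmasked.

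Section 2.B already allows a coordinator to call, so no new category of staff is needed. The cost is a small scheduling limit on who calls at small sites, and care in keeping the arm off the form. The SAP is written in the past tense; if the calls have already been made, the report should state who called and who graded, whether they knew the arm, and that this is a limitation.

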Site monitoring visits will be performed by the sponsor investigator's authorized representative on a regular basis, pursuant to the Monitoring Plan. During these visits, information recorded on the CRFs will be verified against source documents. Additional computer programs that identify selected protocol deviations, out-of-range data, and other data errors within the electronic data entry may also be used to help monitor the study. As necessary, requests for data clarification or correction will be sent to the appropriate site PI.

Independent auditors from the sponsor investigator's authorized representative will be allowed by the site's PI to audit. In addition, audits may be conducted at any time by appropriate regulatory authorities and/or the IRB.

Data Collection

- Demographic data collection (Appendix AP3)
 - o Age
 - o Sex
 - o BMI
 - \circ $\,$ Tumor location and size $\,$
- Likert Scale for technical evaluation (Appendix AP4)
- Adverse event collection (immediate/delayed complications- Appendix AP5/6)

At UCD, eligible patients who consent to the study will have their data captured in a password protected database through Redcap. Protected Health Information will be de-identified after extraction, and each subject assigned a unique random number. This database will be stored in a password-protected database, in a password-protected folder on the secure server behind the UCD firewall. The information will, at all times, only be able to be accessed by the primary investigator and co-investigators. All study personnel have completed HIPAA and CITI training in human subjects' research. In order to de-identify patients from their health information a spreadsheet will be created that assigns a number to each patient. The legend will be stored separately in a password-protected folder for patient numbers. Once the data COMIRB Protocol #14-1711 PI: [name] MD Version Date: 01/23/2019

collection is complete the spreadsheet containing the names and numbers will be destroyed. The deidentified information will be stored on a secure server behind the UCD firewall and will be password protected.

Regarding multicenter data, any institutional data will be shared via encrypted email to the primary site (UCD). At UCD, the Case Report Forms will be reviewed by UCD's investigators and study coordinators periodically throughout the conduct of the trial to review adverse events

D. Potential Scientific Problems.

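### Adverse events are graded Minor or Major by event name alone, so the grade does not track consequence and some events have no grade

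*Protocol*

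**What the plan says.** Protocol section 2.C, Recording of Complications, starts from a broad definition: "Complications will be defined as any deviation from the clinical course after the procedure". It continues: "All adverse event data will be collected during the study period and graded as", followed by two categories. Minor is "nausea, vomiting, abdominal pain". Major is "perforation, pancreatitis, major bleeding, infection, transfusion secondary to major bleeding, aspiration, arrhythmia, hypotension, death".

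The next paragraph adds two further assessments. One is of severity and causality: "The investigator at each site will assess each adverse event with respect to severity and relationship to the study interventions". The other is of seriousness: "Those adverse events that meet the criteria for a Serious Adverse Event will be reported additionally on a Serious Adverse Event CRF". The supplied text gives no scale for the first and no criteria for the second. The Data Collection list in the same section refers to a form that was not supplied: "Adverse event collection (immediate/delayed complications- Appendix AP5/6".

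The secondary endpoint in section 2.B is "Adverse event rates recorded throughout the study period", with no mention of grade. Section 2.E plans Fisher's exact test on the adverse event rate, again without a split by grade. The SAP contains no grading of adverse events.

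**The concern.** A severity grade should tell the reader how badly patients fared. Here it records only what the event was called. The same name can cover a trivial episode and a grave one, and an event whose name is on neither list cannot be graded, although the protocol says all of them will be.

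Hypothesis 2 in section 1.2 is that the preloaded needle keeps adverse event rates comparable with the back-loaded needle. Any statement that the events in the two arms were also of similar severity would rest on Minor/Major, because that is the only grading the supplied documents define. Each site's investigator would also have to settle the unlisted and borderline events alone, and a descriptive comparison across sites is itself a listed endpoint.

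**Working it through.** The plan states no figure on this point to reproduce. The check applies the two lists to example events, looks for any other rule, and follows the grade into the planned analysis.

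**1. Inputs.** Section 2.C gives three Minor names and nine Major names. Only bleeding carries a severity word (major), and that word is not defined. Hypotension and arrhythmia have no threshold or duration. No residual category and no rule for upgrading an event are stated. Sample size is 20 per arm (section 2.E and the SAP).

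**2. Applying the lists.**

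| Event after the procedure | On which list | Grade as written |
|---|---|---|
| Abdominal pain leading to admission | Minor | Minor |
| Brief, self-limited hypotension in recovery | Major | Major, as for death |
| Non-major bleeding | Neither | None |

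The third event is a deviation from the clinical course and so counts as a complication, yet the grading instruction cannot be carried out for it.

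**3. Looking for another rule.** The investigator's severity assessment has no scale and is not said to change the Minor/Major grade. The route for serious adverse events is a separate form. The SAP is silent. Nothing in the supplied text resolves the three cases.

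**4. Following the grade into the analysis.** Take illustrative counts, not taken from the documents: two patients in arm A are admitted for abdominal pain, two in arm B have brief hypotension in recovery, and there are no other events.

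- Overall rate, which is the planned comparison: A 2/20 = 10%, B 2/20 = 10%.
- Major by the lists: A 0/20 = 0%, B 2/20 = 10%.
- Graded so that an unplanned hospital stay ranks above a self-limited episode: A 2/20 = 10% in the higher grade, B 0/20 = 0%.

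The planned comparison does not change. Only the severity breakdown does. If someone did test 2/20 against 0/20, the two-sided Fisher p-value would be 0.49, so at this size the breakdown would be read as description.

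**5. Bleed and transfusion.** These are two entries on the Major list for one clinical episode. Section 2.E does not say whether adverse event rates count patients or events. One patient with both gives 1/20 = 5% if patients are counted, and two entries over 20 patients, 2/20 = 10%, if events are counted.

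**The case against.** The strongest reply is that no planned analysis uses the grade. The hypothesis, the endpoint and the Fisher test all concern the overall adverse event rate. That stands. A reader might infer from the Major line in step 4 that the grading could put the arms in the wrong order in the safety comparison. The documents do not support this, because no comparison of Major events is planned and the planned one gives 10% in each arm.

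A reader might also infer that the Data and Safety Monitoring Committee would be misled by the grade. The Monitoring and Oversight text of section 2.C sends it serious adverse events, unanticipated problems, device effects and adverse events, and does not mention Minor/Major.

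Nor should a marker lost outside the tumour be offered as an ungraded event: migration and inadvertent deployment are separate endpoints in section 2.B. A low pressure reading during the procedure is a weak example too, since complications are defined as arising afterwards. That is why recovery is used above.

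The reply also notes that an admission for pain may still be caught by the severity assessment or on the form for serious events. That is fair. An event that is Minor by list and serious by outcome is not a contradiction, because these are different attributes. But without a scale or a link between them, the reported grade remains the one from the lists.

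Finally, Appendix AP5/6 might hold definitions or a field for other events, and the protocol does not call its lists exhaustive. Neither can be checked here, and this lowers confidence.

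**Conclusion.** The point holds for the Minor/Major grade as written in the protocol body. It misgrades events whose consequence differs from what their name suggests, and it leaves some complications without a grade. The harm is limited to the severity description that would accompany a statement of comparable safety, and to consistency between sites. The primary endpoint and the overall Fisher test are not affected. In the illustration, two patients per arm are enough to move the Major rate between 0% and 10% by choice of rule, while the overall rate stays at 10%.

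Severity is minor. Confidence is moderate, because the conclusion assumes that Appendix AP5/6 and the criteria for serious adverse events, neither of which was supplied, contain no rule that links severity to Minor/Major or covers unlisted events. If they do, the remaining task is to state that rule in section 2.C.

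**What to change.** Keep the listed names as event types and stop using them as the grade. Grade every event, listed or not, by its consequence, for example unplanned or prolonged hospital stay, intervention needed, permanent harm, or death. Use the investigator severity assessment that section 2.C already requires, and write its scale into that section. Report by arm the number of patients with at least one event, overall and at each grade, so that a bleed and its transfusion count once. Tabulate event types underneath.

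The cost is a small change to the protocol text and the adverse event form. The form was not supplied, so the exact change to it cannot be sized. The Minor/Major split would be less directly comparable with reports that use name-based lists; the type table softens this. The SAP is written in the past tense, so the grading may have to be done from records already collected. If so, the report should say that the grade was assigned retrospectively.

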Currently, back-loading the fiducials is the only option for preparing delivery of fiducials via the EUS approach. Difficulties associated with fiducial loading and deployment can increase procedure duration due to cumbersome fiducial back-loading, fiducial misplacement & migration, as well as inability to pass the fidicual marker through the needle due to endoscope angulation.

Multiple observational studies ranging from 7 to 57 patients have sited a technical success rate of 86-100% using 19 and/or 22 gauge needles [8,10-14, 17-19], with average procedure time between 7-12 minutes [12] using the fiducial back-loading technique.

A new mode of fiducial delivery has recently been developed that hopes to circumvent some of the technical issues inherent to traditional fiducial marker loading and deployment. In a feasibility study by Draganov et al, a prototype 22-Gauge EUS needle preloaded with four fiducials were used in a porcine model to test ease of deployment, technical success, accuracy, EUS visualization of the needle, fiducial visualization on EUS as well as fluoroscopy and CT, as well as time for placement and adverse events. Fiducial deployment was successful 95.6% of the time with all 172 fiducial markers deployed on predetermined targets. Using a 5 point Likert scale, needles were deemed easy to pass, relatively easy to COMIRB Protocol #14-1711 PI: [name] MD Version Date: 01/23/2019

deploy, and easily visualized on EUS, with excellent fluoroscopic and CT visualization. In addition, time for deployment was on average less than 60 seconds.

To date, there is no randomized controlled trials comparing total duration of time needed for placement of fiducials using the traditional back-loading technique of fiducial markers to the new preloaded needles in regards to EUS based fiducial marker placement for IGRT in pancreatic cancer.

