Factors that could threaten our ability to obtain meaningful generalizable knowledge from this study would be lack of patient followup to reevaluate fiducial marker location. However, as patients are having this procedure performed for cancer therapy, it is unlikely that there will be a large proportion of patients who are lost to followup.

E. Data Analysis Plan. This section should include:

For Quantitative analyses:

i) Statistical Analysis: Categorical variables will be summarized with counts and percentages whereas continuous covariates will be summarized with means and standard deviations (SD). For evaluation of the demographic data a Fisher's exact test or Mann-Whitney U test will be performed as applicable.

ii) Success rates for each of the two arms will be calculated as a proportion of number of successfully deployed fiducial markers over the total number of patients in whom this was attempted within the study population. This will be reported as a percentage. Comparison of successful deployment of fiducial markers by two comparative groups will be performed by Fisher's exact test. Similarly, comparison between the two arms will be performed for technical success, procedure time, adverse event rate, rate of migration, ease of fiducial deployment, and visualization of needle and fiducials via EUS and CT by using Fisher's exact test. When data is ordinal, comparisons will be made using Mann-Whitney U test.

Sample Size:

Sample size calculated for the primary aim showed that in order to detect that the PreLoad4 device can be delivered in at least 60% of the time it takes to deliver a fiducial marker by back-loading, for an 80% power and alpha of 0.05 (two-sided) a minimum of 20 patients will be required in each arm.

Randomization:

Patients will undergo central block randomization (5 blocks of 4 per stratified arm at each center) stratified based on tumor location (head/neck vs. body/tail). This will be performed by a computerized binary number generator at the University of Colorado, who will control randomization for all sites. The arm that the patient will be randomized to will be determined by the above process and with the use of opaque sealed envelopes.

F. Summarize Knowledge to be Gained.

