## Statistical Analysis Plan

The sample-size calculation was based on limited experimental data in a porcine model, and on a consensus decision among expert endosonographers regarding the relative reduction in the time (60%) to deploy preloaded fiducial markers. We estimated that a sample size of 40 patients (20 in each arm) was needed to provide the study with at least 80% power and a 2-sided alpha of 0.05. All analyses were performed according to the intention-to-treat principle. Per-protocol analysis was also performed. Descriptive statistics are reported as absolute values (percentage), mean 2 standard deviation, and median (IQR), as appropriate. Comparisons of baseline characteristics and outcomes were evaluated using chi-square or Fischer exact test for categorical data and Student t test or Mann-Whitney U test for continuous data. Pre-established subgroup analysis was performed by tumor location (head/neck vs body/tail). Although not pre-established in the study protocol, results were also stratified by time of randomization (first half vs second half) to explore a possible learning curve effect. Statistical significance was defined as P <.05. All statistical analyses were performed using Stata/ IC version 12.1 (College Station, TX).

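### The primary time comparison is planned unadjusted although tumour size is collected and tumour location stratifies the randomisation, and the planned baseline tests do not guard against chance imbalance

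*Protocol*

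**What the plan says.** Protocol 2.E plans tests on the baseline data: "For evaluation of the demographic data a Fisher's exact test or Mann-Whitney U test will be performed as applicable". The data collection list in 2.C shows which variables these are: age, sex, BMI, and "Tumor location and size".

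The SAP treats baseline and outcome variables together: "Comparisons of baseline characteristics and outcomes were evaluated using chi-square or Fischer exact test for categorical data", with a t test or Mann-Whitney test for continuous data and a single 5% threshold. Protocol 2.E likewise lists only two-group tests for the outcomes, procedure time included. Neither document names a covariate, an adjusted model, or a rule for handling an observed imbalance.

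Tumour location is handled in the design. Randomisation is blocked within centre and stratified by head/neck versus body/tail, and the SAP has a subgroup analysis by location. Tumour size is neither stratified on nor used in any outcome analysis.

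The sample size in the protocol is "for an 80% power and alpha of 0.05 (two-sided) a minimum of 20 patients will be required in each arm". The SAP agrees: "We estimated that a sample size of 40 patients (20 in each arm) was needed".

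**The concern.** In a randomised trial any baseline difference arises by chance, so a significance test of baseline balance addresses a null hypothesis already known to be true. It is also a poor balance check in a small trial, because a large imbalance can be non-significant. What matters for the result is the size of the imbalance multiplied by the strength of the variable's link with the outcome. The baseline P value measures neither.

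The plan uses the unadjusted comparison whatever the baseline table shows. If larger tumours take longer to mark, or are easier to mark, a chance difference in tumour size passes into the primary result in full. If size explains part of the variation in time, leaving it out also costs power that 40 patients could otherwise provide. Separately, the trial stratifies by location but does not carry the stratum into the analysis. Any variation between strata that the design has balanced then still inflates the standard error.

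**Working it through.** **Inputs from the documents.** 20 per arm, 80% power, two-sided alpha 0.05. **Assumption.** The correlation r between tumour size and log placement time is not given; I use 0 to 0.5. A t test stands in for the planned two-group test, and all effects are in SD units.

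**1. The plan's own figure.** No SD is stated, so 20 per arm cannot be reproduced. Solved backwards, the detectable effect is (1.960 + 0.842) × √(2/20) = 0.886 SD by the normal approximation, or 0.909 SD by the t test. The protocol describes delivery in "60% of the time it takes to deliver a fiducial marker by back-loading", a 40% reduction, which implies a coefficient of variation of 0.4/0.886 = 0.45. The SAP speaks of a consensus "regarding the relative reduction in the time (60%) to deploy preloaded fiducial markers", which implies 0.6/0.886 = 0.68. That difference is a separate matter and does not affect what follows.

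**2. What a baseline test can detect.** The smallest significant difference is t(0.975, 38 df) × √(2/20) = 2.024 × 0.316 = 0.64 SD. A 0.6 SD difference gives t = 0.6/0.316 = 1.90 and is not significant. For a binary variable such as sex, Fisher's test gives P = 0.11 for 8/20 versus 14/20 and P = 0.054 for 5/20 versus 12/20.

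**3. How often such imbalance arises.** The standardised difference is approximately N(0, 2/20).
- At least 0.3 SD: 34% of trials.
- At least 0.5 SD: 11%.
- At least 0.6 SD: 2 × (1 − Φ(1.90)) = 5.8%.
- At least 0.64 SD: 4.3%. So 5.8% − 4.3% = 1.5% fall between 0.6 and 0.64 SD.

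**4. Carry-over of a 0.6 SD imbalance.** The shift in the arm difference is 0.6r. Given the imbalance, the standard error is 0.316 × √(1 − r²), and the unadjusted test rejects beyond ±1.960 × 0.316 = ±0.620. The conditional false-positive rate is therefore P(Z > (0.620 − 0.6r)/SE) + P(Z < (−0.620 − 0.6r)/SE).

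| r (assumed) | Shift, SD | Share of 0.909 | SE | Conditional false-positive rate |
|---|---|---|---|---|
| 0 | 0 | 0% | 0.316 | 5.0% |
| 0.2 | 0.12 | 13% | 0.310 | 6.2% |
| 0.3 | 0.18 | 20% | 0.302 | 7.6% |
| 0.5 | 0.30 | 33% | 0.274 | 12.2% |

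Simulation agrees: about 8% at r = 0.3 and 12% at r = 0.5.

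Conditional power moves in either direction. If the imbalance works against the device, power is P(Z > (0.620 − (0.886 − 0.6r))/SE), which is 61% at r = 0.3 and 45% at r = 0.5. If it favours the device, the corresponding figures are 93% and 98%.

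**5. Averaged over all randomisations.** The simulated false-positive rate of the unadjusted test is 5.1% (r = 0.3) and 4.8% (r = 0.5), so it is valid.

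**6. Effect of adjustment.** With size in the model, the conditional false-positive rate returns to about 5%. Simulated overall power, against 80% unadjusted, is about 79% at r = 0, 80% at r = 0.2, 82% at r = 0.3 and 89% at r = 0.5.

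**The case against.** A reader might infer that the baseline tests act as a screen that decides whether an imbalance is corrected. The documents do not say so. No analysis depends on a baseline P value, a significant imbalance would go uncorrected just as a non-significant one would, and deleting the tests would change no primary result. This stands, and it separates two matters: baseline P values are a reporting weakness, while the missing adjustment is what affects the result.

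A reader might also infer that the baseline data serve no other purpose, or that location is left to chance. Neither is right, since location is the stratification factor and has its own subgroup analysis. The argument about imbalance applies to unstratified variables, chiefly tumour size.

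The strongest objection concerns size of effect. The unadjusted test holds 5% overall, imbalances of 0.6 SD or more are uncommon, and the correlation is assumed. It could well be weak: in protocol 2.B the clock starts when the needle leaves its packaging, so the time includes manual back-loading outside the patient, which tumour size cannot influence. At r = 0.2 the conditional error is about 6% and the power gain negligible. All of this stands. It limits the benefit, but it does not favour the unadjusted analysis, which gains only about one point of power even when r = 0.

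Finally, the SAP is written in the past tense. If the results are already known, replacing the primary analysis would itself be a post hoc choice. This also stands, and the fix allows for it.

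**Conclusion.** The point holds as a low-cost improvement to the primary analysis. It is not an error in any stated figure and not a threat to the validity of the randomised comparison. A reader might take the 8% to 12% as the trial's false-positive rate. It is not: it applies only given a 0.6 SD imbalance in tumour size and an assumed correlation of 0.3 to 0.5.

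Under that assumption the imbalance would move the estimate by 20% to 33% of the detectable effect, and routine adjustment would gain about 2 to 9 points of power at the same sample size. At a correlation of 0.2 or less there is little to gain. What does not depend on the assumption is that a non-significant baseline test at 20 per arm is not evidence of comparability, and that the plan neither acts on such a test nor adjusts for the factor it stratifies by.

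**What to change.** In protocol 2.E and the SAP, define the primary analysis as a linear model of log placement time on arm, with the tumour location stratum and tumour size (continuous, measured before the procedure) as fixed covariates. Include both whatever imbalance is observed, and keep the unadjusted comparison as a sensitivity analysis. If the data have already been analysed, leave the planned comparison in place and report the adjusted model as a labelled sensitivity analysis.

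Report baseline data descriptively, with standardised differences if wanted. Do not use baseline P values as evidence of comparability or to choose covariates.

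The cost is a change of wording and about one degree of freedom per covariate out of 40 patients. If tumour size proves unrelated to time, the loss is about one point of power. No extra patients are needed.
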